## 7. Research Plan for Study 2:

- **Study Design.** Study 2 will address Specific Aim 2 and will involve a nested, group-randomized controlled design, recruiting adolescents from ASPs, such as the Boys and Girls Clubs in Florida. In a 2 (condition) by 4 (time) design, 4 clubs minimum will be randomly assigned to one of two conditions named “ASPIRE” and “GSA-ASPIRE-Network”. Additional ASPs may be recruited in case sample size is not reached.
- Similar to a “wait-list” group, participants in the “ASPIRE” group will receive the GSAs and Network (GSA-Network) portions of the program about 4 weeks following Survey Assessment 4 (A4), between Assessments 5 and 7, in 5 to 7 sessions (5 regular sessions and up to 2 booster sessions). This will include 4 additional assessment points following Assessment 4. With 4 additional assessment points following Assessment 4, we will get to examine improvement over time following participants' engagement in the social features of the program. Participants in the ASPIRE-only group did not have the opportunity to engage with these social features of the program during the Fall.
- To assess long term success among participants in the “GSA-ASPIRE-Network” group, 2 assessment points will be added to this group (A5 and A8 only).
- Survey assessments A5 through A8 will be the same as the network assessment survey (Appendix 4).

- **Eligibility.** An ASP is eligible if it provides internet connection at its club and houses at least 10 adolescents. Adolescents will be eligible if (1) they are of ages 11-18 years, (2) they are members of ASP, (3) they are English-speaking, and (4) have not participated in an educational program about tobacco in the last year. Adolescents with developmental disability, mental or physical, are not excluded from the study. However, they will only be able to participate if (1) they understand the information presented to them in the consent document, and (2) they believe they are capable to engage in the board game, use the internet, and answer survey questions.
- **Methods for Study 2.** The following section describes the methods being used and step-by-step procedures to conduct the study.
  - **Final design of the GSAs:** First, the game-based social activities (GSAs) will be developed and printed by working closely with the development company, expert in social action and education. The development company is called Toolbox for Education and Social Action (TESA). There is no connection with them other than through this research project. Based on 3 focus group discussions conducted in Houston, Texas through a previous institution, adolescents reported preference for

social interaction through cooperation, a narrative guiding their advancement through activities, and the use of strategy for education. As a result, the GSAs will be developed in the form of a cooperative tabletop board game, which will include a set of cards with GSAs and a series of challenges to overcome on a game board. The learning process occurs through 4 sets of cards and activities: trivia (answer multiple-choice questions, fill in the blank, and reorder words), discussions (discuss difficult situations), and interactive activities during and outside of the board game sessions (charades, drawing, miming, role playing to understand tobacco scenarios, arts and crafts projects, journal entries, practicing stress reducing techniques). Some activities will be completed outside of the session (appendix 13). The cards and activities have 3 teaching goals: friendship building, tobacco prevention, effects on the environment, and advocacy. Any changes in the kinds of GSA activities uncovered by Study 1 (e.g., adding a physical activity) will be described in a revision to the study before implementing.

- **Final design of the GSAs during COVID-19:** In case ASPs are not allowing their adolescent members meet in person at their sites, we plan to use a web-based version of the GSAs that we will develop with a team of computer scientists. The computer science team will create the web-based GSAs to incorporate all aspects of the GSAs created by TESA. While overseen by the Integrated Risk Management (IRM) team at the University of Florida, the computer science team will develop the web-based version while complying with UF security and privacy guidelines and policies. The web-based GSAs will have a secure built-in video-conferencing system to ensure that participants can communicate with one another as well as the research team. The web-based GSA will also have the ability to record sessions, administer questionnaires, and collect activity entries for the purpose of data collection. Appendix 12 shows a mock picture of what is envisioned for the web-based GSAs. Any changes in the web-based GSAs based on the recommendations of IRM and the computer science team will be described in a revision to the study before implementing. In addition to the web-based GSA, the TESA team may make the boardgame playable online by creating the boardgame in an online portal for virtual boardgames known as Tabletopia. The use of Tabletopia will not be done without a risk assessment completed by Integrated Risk Management (IRM).

- **Connection with ASP sites:** At first, as many as a minimum of 20 ASPs such as the Boys and Girls Clubs in Florida and schools such as PK Yonge school will be approached for this study. The PI and/or study staff will attend ASP sites, in order to present the study to program directors and describe to them the study procedure.

Once ASPs are recruited, we will obtain letters of support (Sample in Appendix 0) or a Contract for Services (Sample in Appendix 15) from these ASPs. Signed letters of support or Contract for Services will be submitted to IRB. We will not move forward with data collection from adolescents unless signed letters of support are obtained from the ASPs.

- **Consent procedure:** If the ASP directors agree to have their program site participate in Study 2, they will complete and sign a letter of support or Contract for Services. Then, the PI and/or study staff will verbally announce the study to adolescents in a private classroom setting, in the presence of ASP staff. Interested adolescents will be presented with all information concerning the study (study purpose, requirements, risks, and benefits of participation) and will be given a form to share with their parents (Appendix 1e). When parents register their child for the ASP Summer Camp, research staff will attend the ASP Summer camp registration in-person, virtually, or over the phone to discuss the project and review the consent form with parents.
- If the location has ended their Summer registration before research staff could be present, ASP staff will contact parents with eligible adolescents to discuss the project. If parents are interested, ASP staff will send research staff contact information of the parent. ASP staff will use a script to discuss the project with parents (Appendix 16). ASP staff will share contact information in an encrypted excel spreadsheet.
- When parents/legal guardian arrive to pick up or drop off their adolescents at the ASP, they will be approached concerning the study and all informed consent information will be presented to them verbally and on iPad screen.

- Research staff may also announce the study to parents at a parent orientation hosted by the ASP. In this case, parents will be approached to review and sign the informed consent form after the parent orientation.
- After obtaining parental permission, the interested adolescent will be presented with the assent form to sign in the presence of a witness (a staff from the ASP). An adolescent may sign a one-page assent form in place of the assent portion of the informed consent form.
- Emancipated adolescents (age 18) will be asked for parental permission in cases where ASPs ask for parental permission from adolescents of the age 18. Emancipated adolescents will be asked to sign a complete consent form or a one-page consent form in its place. All such procedures will occur in a private room at the ASP.
- Parents will use the iPad to review the consent and provide an electronic consent. Adolescent will also assent on the iPad. However, paper consent forms will be available in case parents or adolescents prefer a paper-based form. Both parents and adolescents will receive a copy of the consent document for their own records.
- For parents that are hard to reach, ASP staff will send the adolescent home with a one-page parent permission consent form for the parent to review and sign. Once parental permission is obtained, research staff will review the child assent with the adolescent and obtain their assent.
- Adolescents ages 11-17 will review and sign the child assent with study staff either in-person or remotely.

For sites that require parent permission for 18-year-old adolescents to participate in extracurricular activities, ASP staff will send the adolescent home with an informed consent form or a one-page parent permission form for the parent to sign. Once the parental permission is obtained, research staff will review the informed consent form or the one-page consent form specific to 18-year-old adolescents with the 18-year-old adolescent.

A separate consent form has been created for 18-year-old adolescents. Following our announcement at the ASP, if an adolescent who is 18 years of age expresses interest in the study, we will approach this individual during breaks at the ASP to go in detail over the consent form.

- It is expected that 800 adolescents and their parent/legal guardian from about 15 ASPs will be interested and eligible. Parental permission and child assent forms will be presented in-person, and in details by a study staff or the PI. A staff member of the ASP will act as witness during consent.
- After recruitment, we will schedule dates with the ASP in order to conduct the study.
- **Consent procedure for study 2 during COVID-19:**  
Due to COVID-19, we will be reviewing the study information and assents/consent forms with adolescents and parents remotely via phone call or Zoom should the ASP not allow research staff, adolescents, or their parents inside the facility. Research staff will contact participants using Cisco Jabber.

If parents and adolescents are allowed to be at the ASP facility, research staff will review the consent form with parents and adolescents in person. Parents and adolescents will be given the option of signing a paper consent form to review and sign with the guidance of PI and/or study staff.

If the ASP director agrees to have their program site participate in Study 2, they will complete and sign a letter of support or Contract for Services that can be available electronically.

Through ASP recruitment, the ASP will distribute an announcement (Appendix 1e) to parents via e-mail. ASP staff may also announce the study to adolescents in need of parent permission via email using the informational form (Appendix 1f). On the other hand, through HealthStreet, ResearchMatch, and Facebook, parents will be approached directly by study staff with the study announcement.

If PI and/or research staff cannot be at the ASP in person with adolescents, research staff will announce the study to the adolescents in a private classroom setting using Zoom in the presence of ASP staff. After the announcement, ASP staff will provide interested adolescents with an informational form to give to their parent about the study (Appendix 1e). The parent may contact research staff using the contact information on the form. During the phone or Zoom call, interested adolescents and parent/legal guardian will be given a link to the online consent form to review and sign with the guidance of the PI and/or study staff. Research staff will contact participants using Cisco Jabber or Zoom.

Adolescents of age 18 will be sent an announcement (Appendix 1g) by ASP. If the 18-year-old adolescent expresses interest to PI and/or study staff, he/she will be invited to a phone call or Zoom meeting to discuss the research study. They will be sent a complete online consent form to review and sign with the guidance of the PI and/or study staff. Research staff will contact participants using Cisco Jabber.

For parents that are hard to reach, ASP staff will send the adolescent home with a one-page parent permission consent form for the parent to review and sign. Once parental permission is obtained, research staff will review the child assent with the adolescent and obtain their assent.

For sites that require parent permission for 18-year-old adolescents to participate in extracurricular activities, ASP staff will send the adolescent home with an informed consent form or a one-page parent permission form for the parent to sign. Once the parental permission is obtained, research staff will review the informed consent form specific to 18-year-old adolescents with the 18-year-old adolescent.

The parents and adolescents will be given the option to download an electronic copy of the signed online informed consent form for their own records or a copy of the one-page parent permission consent form that they reviewed.

Parents and adolescents may use their computers to sign the e-consent.

If research staff are to work with parents, adolescents, and ASP staff inside the ASP facility, research staff will follow COVID-19 guidelines put in place by the ASP. Research staff will wear masks, use hand sanitizer, and will distance themselves from others by at least 6 feet. If someone at the facility were to test positive for COVID-19, all who were in contact with the positive case will be required to quarantine for 2 weeks.

[figure not shown]
It is expected that 1000 adolescents and their parent/legal guardian will be interested and eligible. Parental permission and child assent forms will be presented online, and in detail by a study staff or the PI.

Both program implementers and ASP staff members will receive adult consents to participate in focus group discussions and interviews.

- **Baseline assessment at Day 1:** In a classroom setting, participating adolescents will be invited to complete the baseline 20-minute psychosocial survey (time 1) and the baseline 20-minute social network survey (time 1).
- **Randomization at Day 1:** Immediately after baseline assessment at Day 1, the participating clubs will be randomly assigned to either ASPIRE or GSA-ASPIRE-Network. Details on each intervention are described in the following sections. After-school programs (ASPs) will be randomized in a single-blinded format to 1 of 2 conditions: the ASPIRE program or the GSA-ASPIRE-Network program. We will use a covariate-constrained approach in randomizing ASPs to minimize between-group differences in club characteristics (e.g., adolescent volume in a cluster, proportion of adolescents with intent to use tobacco or users, age, gender).

- **Orientation at Day 1:** Also, after baseline assessment at Day 1, participants will receive a session of orientation, allowing them to learn how to take part in the program (ASPIRE or GSA-ASPIRE-Network), depending on their assigned condition. The orientation will be in the form of a presentation and some attempts at engaging in the program for the first time.
- **Intervention details:** The first session of the assigned intervention (ASPIRE or GSA-ASPIRE-Network) will occur three to five days after orientation (depending on the ASP's availabilities).
  - › In the ASPIRE condition (other treatment), participants will engage in five 70-minute sessions of ASPIRE spread over a period of 5 weeks (1 session per week). During each session, participants will alternate between 10 minutes of ASPIRE use and 5-minute breaks.
  - › In the GSA-ASPIRE-Network condition (intervention), on the other hand, participants from each club (expected to be between 24 and 50 participants) will be purposely seated in groups, with 3 to 6 adolescents per group. Participants' group allocation will be determined based on findings from social network analysis (details below). Each group will engage in five 70-minute sessions of ASPIRE spread over 5 weeks (1 session per week). During each session, participants will either receive ASPIRE, or the GSAs, or both. Along with the game board, GSA content will be presented to participants via the "Kahoot! 360 Pro" platform. Study data will not be captured nor stored on Kahoot. Participants will not complete any assessment question of identifiable questions via "Kahoot!". They will engage in the program as a team. After each session, with a timeline of a week, participants will have the opportunity to engage in off-session activities at their own pace. These activities will allow participants to practice what they learn during the sessions. To receive credit for completing the activities, participants will be asked to keep track of their progress in these activities and present evidence of completing the activities. To this end and depending on the activities, they may record themselves completing the activity via photo or video and submitting the recording to the research team via the secure system REDCap. Recording and submitting the photos or videos will not be required to participate in the research project, and alternative methods of presenting evidence of activity completion will be provided. If participants choose to submit videos or photos for their activities, they will be asked to capture these videos and photos without having a non-participant in the background. If a non-participant is visible in the background, the recording will be censored to remove the non-participant.
  - › Adolescents who decline to be part of the study will engage in the usual ASP activities provided by the ASP staff. These activities are comparable to the "control" (non-network) condition, but without the surveying.
- **Additional assessment points:** In addition to baseline (time 1: Assessment 1), all participants will complete psychosocial surveys and social network surveys after 3 sessions (i.e., mid-intervention; time 2: Assessment 2), following the last session (i.e., post-intervention; time 3: Assessment 3), and 2 to 3 weeks post-intervention (i.e., follow-up; time 4, or assessment 4). After time 4, we will conduct one-on-one interviews with 60 adolescents randomly selected from ASPIRE (n=30) and GSA-ASPIRE-Network (n=30). We will also conduct exit interviews with 2 ASP staff members per ASP and all program implementers. Exit interviews and the intervention sessions will be audio-recorded, in order to capture user's experience. Survey assessments 5 through 8 will also be completed as delineated in the above study design for Study 2. Figure 1 presents the study flow diagram.

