**Primary Outcome for Study 2:**

- **Intention to use tobacco** is defined as intention to use any tobacco product (cigarettes, cigars, hookah water pipes, and vaping products) in the near future.

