**Figure 1. Study Flow Diagram**

**Note:** Approximate days: Assessment 1 and orientation at day 1 (time 1, baseline), session 1 at 3-5 days after assessment 1, session 2 and assessment 2 (time 2; mid-intervention) at day 12, session 3 at day 19, session 4 and assessment 3 (time 3, post-intervention) at day 26, and assessment 4 (time 4 or assessment 4, follow up) at day 56, assessment 5 at 1 month after assessment 4, Assessment 6 immediately after GSA-Network, assessment 7 at 2-3 weeks later, and assessment 8 at 1 month after A7.

- Instruments for Study 2.** Several variables will be measured through psychosocial (Measures in Appendix 3), and social network surveys (Appendix 4), using previously validated measures delineated below. In a private classroom setting, a study staff or the PI will conduct and collect the surveys and audio recordings.

- **Psychosocial survey:** At all 4 time points, the psychosocial survey will measure tobacco use status and intention to use tobacco. At time 1, this survey will include psychosocial determinants of smoking and factors that may affect an online experience, social influence, social activity engagement, and game play. At time 3 only, the psychosocial survey will include measures to check for any expected differences and similarities between groups (i.e., manipulation check): Attitude toward the intervention, perceived medium interactivity, perceived social interactivity, and perceived entertainment value. To capture adolescents' tendency to positively influence others, the survey will measure interpersonal communication, ability to persuade others, and diffuse health information to others.

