- **Social network survey:** At all 4 time points, the social network survey will present a list of names of all participants in the classroom. They will be asked to pick and write the names of their six best friends at their club. Best friends are defined to adolescents as "people your age with whom you feel at ease and can talk about personal matters". To measure friendship strength, the survey will ask the respondent to rank nominated friends from strongest to weakest friendship (coded 1 through 6). To measure positive influence, the survey will ask the respondent: (1) how likely he/she may ask each nominated friend for general advice, (2) how likely he/she may accept a tobacco product when offered by each nominated friend (reverse coded), and (3) how likely he/she may avoid a tobacco product when advised by each nominated friend. The strength of a tie between the respondent and each nominated friend will be: Friendship strength × Positive influence. Tie strength will allow the structuring of the social network for each club. Based on the social network at time 1, adolescents will be grouped for their intervention sessions. The survey will also consider participants' nominated advisors and leaders in their ASP. Positive social influence is defined as connection with and support from others who do not intent to use tobacco.
- **Exit Interview questions** (Appendix 5): With adolescents, these questions will address (1) adolescents' most and least favorite elements in the program, (2) their teamwork experience, (3) ways to improve activities, and (4) opportunities for peer-to-peer interaction. With staff members of the ASPs, these questions will address (1) feasibility of the intervention at their location and (2) how they would want to improve the intervention. With intervention implementers, these questions will address (1) feasibility of the intervention, (2) difficulty of implementation, and (3) how they would want to improve implementation.

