Susceptibility to use tobacco is a clinical and epidemiological screening questionnaire of 3 items that has been shown to be the most potent predictor of actual tobacco initiation among adolescents. The continuous version of this scale is termed “intention to use tobacco”. Sample size and power have been calculated based on the hypothesized difference between groups that render participants in the GSA-ASPIRE-Network group non-susceptible to use tobacco, based on the “intention to use tobacco” scale and previous research.

Sample size calculation is done for H1 and satisfies H2. These power estimates are conservative. We will have more power using mixed-effect models. Sample size was calculated based on 2 clusters per arm, however, we will have more power with the proposed 8 clusters (4 clusters per arm). Considering that about 33% of adolescents generally intent to use tobacco, the required sample size is 300 participants. Considering 40% retention and 50 potential non-eligible, we will recruit 800 participants. In addition to this sample size, we will work to reach a representative Florida sample of adolescents. For the interviews, thematic saturation with adolescents is expected by 60 interviews (20% of the final 300 participants).

- **Quantitative data analysis for Study 2.** To test H1, a linear mixed-effect model (LMM) will be conducted to compare the conditions with respect to intention to use tobacco (continuous outcome variable), in a 2 (condition)  $\times$  4 (time) design. Using a second LMM, the 2 conditions will be compared over time with respect to positive social influence. In both models, intervention effects on outcome trajectories over time will be measured with the condition  $\times$  time interaction term. To test H2, a third LMM will be conducted with positive social influence as a mediator. Each individual will be modeled as a random effect nested within the club, club membership will be modeled as a random effect nested within treatment condition, and treatment will be modeled as a fixed effect. If manipulation checks indicate problems, particularly differences or similarities between arms that are not supposed to occur, we will control for such differences or similarities within our models.

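### As described, Assessments 5 to 8 use only the social network survey, so unless Appendix 4 carries the intention items, the later follow-up cannot be judged on the primary outcome

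*Combined protocol and SAP*

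**What the plan says.** Section 7, Study Design, sets out a two-condition, four-time comparison and then adds later assessments. The ASPIRE arm gets four more (A5-A8), so that change after it receives the GSA-Network components can be examined. The other arm gets two more, A5 and A8, with a purpose that begins "To assess long term success among participants in the" GSA-ASPIRE-Network group. The instrument for all of them is fixed in one sentence: "Survey assessments A5 through A8 will be the same as the network assessment survey (Appendix 4").

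The primary outcome, under Primary Outcome for Study 2, "is defined as intention to use any tobacco product (cigarettes, cigars, hookah water pipes, and vaping products) in the near future". The sample size section treats it as the continuous version of a susceptibility scale: "Susceptibility to use tobacco is a clinical and epidemiological screening questionnaire of 3 items".

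Instruments for Study 2 names two separate forms: "Several variables will be measured through psychosocial (Measures in Appendix 3), and social network surveys (Appendix 4"). On the first it says "At all 4 time points, the psychosocial survey will measure tobacco use status", and the same sentence adds intention to use tobacco. On the second it says "At all 4 time points, the social network survey will present a list of names of all participants in the classroom". It goes on to describe six best-friend nominations, a ranking of those friendships, three influence questions about each friend, and nominated advisors and leaders.

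**The concern.** The later assessments exist to show whether benefit lasts and whether the wait-list arm improves once it has the social features. The central hypothesis in the Abstract is that those features lower intention to use tobacco. If the only form given at A5-A8 has no intention scale, neither question can be answered on the outcome the trial is built around.

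A5 matters most. Both arms complete it, and the ASPIRE arm has not yet received GSA-Network. It is therefore the last point at which the arms can be compared as randomised, with one having had the social features and the other not. Intention that is not asked about at A5 cannot be recovered afterwards.

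**Working it through.** No sample size or power figure bears on this point, and the plan gives no figure to reproduce. The check sets the relevant places side by side and counts.

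**Step 1: is any other instrument given for A5-A8?** Two other places in the text mention these assessments as a set to be completed: Additional assessment points (section 7) and the Study 2 data-collection text in section 8. Both only refer back to the study design. The Figure 1 note gives timing, and section 11 gives compensation. None adds the psychosocial survey after A4.

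**Step 2: does the network survey, as described, contain the primary outcome?** Its nearest item asks how likely the respondent would be to accept a tobacco product from each nominated friend. That item is reverse coded and forms part of positive influence, which feeds tie strength. It is specific to a friend and is not the three-item intention scale. Tobacco-use status is not listed either.

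**Step 3: count by assessment, as described.**

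| Assessment | Arms completing it | ASPIRE arm has had GSA-Network? | Intention measured? |
|---|---|---|---|
| A1-A4 | both | no | yes |
| A5 | both | no | not described |
| A6 | ASPIRE only | yes | not described |
| A7 | ASPIRE only | yes | not described |
| A8 | both | yes | not described |

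- ASPIRE arm: 4 + 4 = 8 assessments. Intention at 4 of 8, and at 0 of the 4 added.
- GSA-ASPIRE-Network arm: 4 + 2 = 6 assessments. Intention at 4 of 6, and at 0 of the 2 added.
- With the items added: 8 of 8 and 6 of 6.

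**Step 4: length of follow-up without intention.** The Figure 1 note puts A4 at about day 56 and A5 one month later. With a 30-day month, A5 is at 56 + 30 = day 86. To place A8, assume that the wait-list sessions start at about A5 and run weekly. The plan gives 5 to 7 sessions, A7 at 2 to 3 weeks after A6, and A8 one month after A7.

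- Shortest: 86 + 4 × 7 + 14 + 30 = day 158, which is 158 − 56 = 102 days after A4.
- Longest: 86 + 6 × 7 + 21 + 30 = day 179, which is 179 − 56 = 123 days after A4.

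So roughly 100 to 120 days, including the whole wait-list phase, would have no intention measure. About 30 of those days (A4 to A5) are randomised follow-up. These days are approximate: the text elsewhere puts A4 at 2 to 3 weeks after the intervention, which does not match day 56 exactly. The counts in step 3 do not depend on this.

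**Step 5: the secondary outcome.** The network survey still collects the friend-specific influence items at A5-A8. However, positive social influence is defined through others who do not intend to use tobacco. If that definition is applied literally at A5-A8, peers' intention status would have to be carried forward from A4 or earlier.

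**The case against.** The strongest objection is that Appendix 4 was not available. Section 7 gives a narrative account of the network survey, not an item list, and the form may carry intention items that the narrative leaves out. This stands: the point has to be conditional, and the first action is to look at the form.

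Second, no hypothesis test depends on A5-A8. The H1 model is a two-condition by four-time design, the H2 model names no later times, and intention is measured at all four times. This also stands. A reader might infer that the primary outcome is missing from the primary analysis; the documents do not support that.

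Third, the plan does not define long-term success or improvement as intention. Following the positive-influence items, which underlie the secondary outcome and proposed mediator, is a coherent choice and may have been meant to limit burden. This stands in part. The later data would have a use, but the plan gives no other criterion for success, no reason for dropping intention and no analysis for A5-A8.

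Fourth, the randomised loss is small. A reader might infer that four randomised follow-ups are lost. Only A5 qualifies: A6 and A7 have one arm, and by A8 the ASPIRE arm has had GSA-Network, so A8 compares earlier with later receipt. Nor does the plan itself name A5 as a randomised endpoint.

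**Conclusion.** The concern holds on the text, conditionally on Appendix 4. If the form matches its description in section 7, the primary outcome is absent from every added assessment (0 of 4 in the ASPIRE arm, 0 of 2 in the GSA-ASPIRE-Network arm). Durability and wait-list improvement could then be assessed on the positive-influence items but not on intention. The randomised loss is one time point: follow-up of intention stops at A4, about day 56, instead of A5, about a month later.

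It would go too far to say that the trial certainly collects no intention data after A4, since the form itself has not been seen, or that A5-A8 are uninformative. The consequence is moderate: it limits what can be concluded about persistence and leaves the H1 and H2 tests as planned. It still deserves action before A5, because the omission cannot be repaired later.

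**What to change.** 1. Check whether Appendix 4 includes the intention scale and tobacco-use status. If it does, say so where the network survey is described and in the A5-A8 sentence of the Study Design.
2. If it does not, add those existing Appendix 3 items to A5-A8.
3. Name A5 as a secondary randomised comparison of intention, state its model, and label A6-A8 descriptive.

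The cost is a slightly longer survey and an IRB amendment. The scale has 3 items. If it is asked separately for the four product types in the outcome definition, that is 3 × 4 = 12. The documents do not say which format applies, and they give no item count for tobacco-use status. The A5-A8 contacts are already planned and compensated (section 11), so no new visits or staff are needed.
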